### **8.3 Exploratory Endpoints**

8.3.1 To compare the Cumulus vs. Volpara vs. LIBRA breast density measurement methods to estimate percent change in mammographic breast density from baseline to Month 12 in women applying 2mg of 4-OHT gel per breast vs. placebo.

8.3.2 To perform correlation of drug concentrations in the plasma and the tissue.

8.3.3 To evaluate plasma measurements of Insulin-like growth factor (IGF) pathway members, C-reactive protein (CRP), and estradiol.

8.3.4 To compare the 2D natural vs. 2D synthetic breast density measurement using the Cumulus method to estimate percent change in mammographic breast density from baseline to Month 12 in women applying 2mg of 4-OHT gel per breast vs. placebo.

8.3.5 To evaluate tissue biomarkers (among women undergoing optional pre- and post-treatment biopsies):

- Structure-function activity of TLDUs will be evaluated by counting acinar density.
- Breast tissue density will be evaluated by assessing the patterns of collagen matrix.
- Hormone-mediated cellular activity will be evaluated by measuring the transcriptional expression levels of ER-alpha and ER-associated genes (SETER/PR index).
- Pharmacogenomic response to 4-OHT will be evaluated by measuring Ki67 protein by immunohistochemistry and aurora kinase-alpha gene expression.
- Inflammatory response to 4-OHT therapy will be evaluated by measuring COX2 and p16 proteins, and recruitment of CD68 monocytes by immunohistochemistry.

8.3.6 To examine whether any reductions in mammographic density seen after 1 year of 4-OHT vs. placebo gel application persist at 24 months (or longer under the COVID-19 Contingency Plan), one year after gel application has stopped.

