#### **13.1 Study Design/Description**

A total of 198 potentially eligible participants will be consented and screened for eligibility and, with a conservative estimate, 158 (80%) participants are expected to be eligible. These 158 women will be randomized 1:1 into one of two groups: placebo or 4-OHT gel 2 mg per breast. Treatment will last for 52 weeks. Considering an attrition rate of approximately 19%, we expect to have 128 evaluable women who will have both baseline and 52-week measurements of percent MD of the breast, 64 women in each group.

With 64 women in each group, we will have an 80% power to detect a decrease of percent MD of 6% in treatment group against 2% in placebo group, with a common standard deviation of 8%, using a two-sided t-test with a significance level of 0.05. The proposed difference between the active treatment and placebo groups and the standard deviation are based on conservative estimates from the published work by Cuzick et al. The sample size calculation is performed using nQuery + nTerim 3.0.

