SETER/PR index: estrogen related transcription  
Ki-67, COX-2, p16, CD68.
6. To examine whether any reductions in mammographic density seen after 1 year of 4-OHT vs. placebo gel application persist at 24 months (or longer under the COVID-19 Contingency Plan), one year after gel application has stopped.

All available data will be summarized and analyzed for the secondary analysis. At the end of the study, participant demographic characteristics; the following measurements at baseline and 52 weeks: 1) MD of the breast, 2) tissue biomarkers (among women undergoing optional pre- and post-treatment biopsies: TDLU Involution, Collagen structural changes, SET index, Ki-67, COX-2, p16, CD68, etc.), 3) plasma measurements of parent drug and related metabolite levels and factors related to 4-OHT exposures, such as IGF pathway members, CRP, estradiol, bisphenol and 4-OHT; and the percentage of women with  $\geq 10\%$  absolute decrease in percent MD between baseline and 52 weeks will be summarized using descriptive statistics, such as mean, standard deviation, median and range for continuous variables and frequency/percentage for discrete variables. The difference of continuous variables between baseline and 52 weeks may be compared between two groups using t-test or Wilcoxon rank sum test, whichever is appropriate. Multivariate analogues to the before mentioned univariate tests, such as Hotelling's  $T^2$  test and multivariate multiple regression will be employed when appropriate. Transformation may be performed when necessary to make continuous variables close to normal distribution before evaluating the change of these continuous variables over time between two groups using repeated measures analysis where the intra-participant correlation is taken into consideration, adjusting for other important covariates. In addition, longitudinal data analysis such as the linear mixed effect model will be applied to evaluate the mammogram density change over time. The treatment effect will be evaluated adjusting for other important covariates. The effect of compliance will be evaluated in the per protocol analysis.

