The percentage of women with at least 10% decrease in percent change of MD will be estimated and compared between two groups using chi-squared or Fisher's exact test whichever appropriate. We will also explore the correlation between percent change in MD and other markers using Spearman correlation at baseline or by employing repeated measures analysis when both baseline and 52-week data are included and intra-participant correlation is accounted for. We will also monitor and summarize any adverse events observed in women on this study.

The change in percent MD of the breast from the end of the treatment at 1 year to 1 year after the treatment ends will also be summarized using descriptive statistics, such as mean, standard deviation, median and range for each arm. The difference of this change in percent MD will be compared between two treatment groups using t-test or Wilcoxon rank sum test, when appropriate. Multivariate methods such as simultaneous 95% confidence intervals will be used for estimation purposes when appropriate.

We will define three groups of participants by the menopausal status change during the study, pre-menopausal/pre-menopausal, pre-menopausal/post-menopausal and post-menopausal/post-menopausal, and compare the change of MD and other secondary endpoints among these three groups of participants by Kruskal-Wallis test. We may incorporate this grouping covariate in the repeated measures analysis to evaluate any differential effect of menopausal status change on the change of endpoints by treatment over time. Sensitivity analysis on the treatment effect with and without including women who undergo menopausal transition will be performed. Sensitivity analysis on the treatment effect with and without including women on hormone replacement therapy will be performed. The treatment effect will be analyzed by incorporating the longitudinally measured compliance data as a covariate.

If prior imaging is available (mammogram or other modalities), the data will be collected and summarized. Other statistical methods, such as the MANOVA and multivariate multiple regression, may be used when appropriate.

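### Persistence at Month 24 is addressed by a test of the Month 12-to-24 change, which measures rebound; the plan names no contrast that estimates the effect remaining at Month 24

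*Combined protocol and SAP*

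**What the plan says.** Section 8.3 (item 8.3.6) sets the question: "To examine whether any reductions in mammographic density seen after 1 year of 4-OHT vs. placebo gel application persist at 24 months". Section 13.5 repeats it as exploratory objective 6 and places the assessment one year after the gel stops, or later for women on the COVID-19 schedule: "persist at 24 months (or longer under the COVID-19 Contingency Plan), one year after gel application has stopped".

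The analysis is given later in Section 13.5. The quantity is "The change in percent MD of the breast from the end of the treatment at 1 year to 1 year after the treatment ends", summarized by arm with descriptive statistics. Then: "The difference of this change in percent MD will be compared between two treatment groups using t-test or Wilcoxon rank sum test". The next sentence adds estimation in general terms: "Multivariate methods such as simultaneous 95% confidence intervals will be used for estimation purposes when appropriate".

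Two other parts of the plan bear on the point. Section 13.5 also says that "longitudinal data analysis such as the linear mixed effect model will be applied to evaluate the mammogram density change over time", without naming Month 24 or any contrast. Section 13.6 puts all available data into a repeated measures analysis for the primary and secondary endpoints; persistence is listed as exploratory.

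The plan gives no baseline-to-Month-24 comparison, between-arm difference at Month 24, retained fraction or margin. It also does not say how a non-significant Month 12-24 comparison will be read.

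**The concern.** Persistence concerns what is left at Month 24: the between-arm difference in change from baseline. The specified test concerns what happened after the gel stopped: the between-arm difference in change from Month 12. These are different quantities with different null hypotheses.

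Under the specified test, equal post-treatment change in the two arms is the null. Rejection in the direction of a larger rise on 4-OHT shows the effect being lost. Failure to reject shows only that no differential rebound was detected, which can happen because the effect lasted or because the test could not see a partial loss. A report that follows the plan as written would carry a p-value for rebound and no stated estimate, with uncertainty, of the effect that remains. At stake is how the 24-month result is described. That matters because Section 2.3 presents the trial as preparation for a larger prevention study.

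**Working it through.** **Inputs.** Section 13.1 gives 64 evaluable women per arm, expected decreases of 6 points on 4-OHT and 2 on placebo (difference 4), a common SD of 8, and "using a two-sided t-test with a significance level of 0.05". The documents give no SD for the Month 12-24 change, no correlation between successive changes, and no attrition figure for Month 24. These are assumed below and varied.

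**Formula.** For a two-sample t-test with n per arm, true difference d and SD s, the noncentrality is d / (s × √(2/n)) on 2n − 2 degrees of freedom. At n = 64, √(2/64) = 0.1768 and the two-sided 5% critical value on 126 df is about 1.98.

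**The plan's own figure.** The claim is: "With 64 women in each group, we will have an 80% power to detect a decrease of percent MD of 6% in treatment group". With d = 4 and s = 8, noncentrality = 4 / (8 × 0.1768) = 2.83 and power = 80.1%. The stated 80% reproduces.

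**The planned Month 12-24 test**, for a true 4-point Month 12 effect, n = 64 and s = 8:

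| Share of effect lost by Month 24 | Differential rebound (points) | Power | Non-significant |
|---|---|---|---|
| All | 4 | 80.1% | about 20% |
| Half | 2 | 28.9% | about 71% |
| A quarter | 1 | 10.8% | about 89% |
| None | 0 | 5% | 95% |

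**Sensitivity.**
- SD 6 to 10: non-significant 4% to 39% of the time for full loss, and 54% to 80% for half loss.
- 51 per arm at Month 24 (an assumed further 20% loss) with SD 8: 29% for full loss and 76% for half loss.
- Restricted to trials with a significant Month 12 result (40,000 simulated trials per scenario, correlation between successive changes −0.5, −0.25 or 0): 14% to 20% for full loss and 66% to 71% for half loss. Conditioning on a positive Month 12 finding changes little.

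**What a null rebound result excludes.** The 95% CI half-width is 1.98 × 8 × 0.1768 = 2.8 points. An observed rebound difference of exactly zero is therefore compatible with a loss of up to 2.8 of the 4 points (70%).

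**The contrast that matches the objective.** If each interval's change has SD 8 and the two changes have correlation r, the SD of the baseline-to-Month-24 change is 8 × √(2 + 2r).

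| r | SD of baseline-24 change | 95% CI half-width | P(significant), effect fully kept | P(significant), half kept |
|---|---|---|---|---|
| −0.5 | 8.0 | 2.8 | 80% | 29% |
| −0.25 | 9.8 | 3.4 | 63% | 21% |
| 0 | 11.3 | 4.0 | 51% | 17% |

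If the effect is fully lost, this contrast is significant about 5% of the time, as it should be.

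**The case against.** Several points on the other side are sound.

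- **A reader might infer that the plan will treat non-significance as persistence.** It does not say so. It sets descriptive statistics and, where appropriate, confidence intervals beside the test. The documents support only that a null result could be misread. The 71% is a probability of non-significance, not of a wrong conclusion.
- **A reader might infer that the persistence question cannot be answered from this trial.** That goes too far. The mixed model in Section 13.5 could supply a Month 24 treatment contrast. Among women with all three mammograms, the baseline-12 and 12-24 differences also add up to the baseline-24 difference, so the point estimate can be recovered. What is missing is a commitment to that contrast and its confidence interval.
- **A reader might object that the test cannot tell a kept effect from one that never existed.** That is true of the test alone. But the objective is conditional on a reduction having been seen, and the primary analysis addresses that first.
- **The planned test is not uninformative.** On these assumptions it has about 80% power if the whole effect disappears. Its weakness is partial loss.
- **The replacement contrast does not cure low power.** With half the effect kept it is significant only 17% to 29% of the time, and its interval may be wider than that for rebound. Its advantage is that it estimates the quantity asked about and shows the uncertainty.

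These points limit the size of the concern. The mismatch between objective and specified comparison remains.

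**Conclusion.** The concern holds in a limited form. The only Month 24 comparison spelled out tests differential rebound, while the objective asks about the effect remaining. Non-significance on that test would be weak evidence: about 71% of trials with half the effect lost would show it (54% to 80% for SD 6 to 10), and about 20% of those with all of it lost (4% to 39%). These figures rest on 64 per arm, a true 4-point Month 12 effect, and SDs assumed for the Month 12-24 change. Actual Month 24 numbers and variability may differ.

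The objective is exploratory, carries no stated power or decision rule, and does not touch the primary analysis. The change is still worth making, because it replaces a stated comparison with one that answers the trial's own question.

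**What to change.** Amend Section 13.5 as follows:

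1. Name the between-arm difference in baseline-to-Month-24 change in percent MD, with its 95% CI, as the persistence estimate. Obtain it as a Month 24 treatment contrast from the mixed model already planned.
2. Keep the Month 12-24 change by arm, and its between-arm difference with a 95% CI, as a description of rebound.
3. State that a non-significant Month 12-24 comparison is not evidence of persistence.
4. Account for months since last gel application. On the contingency schedule (Section 7.1.2) the end-of-treatment mammogram falls at Month 13-18 and the later one in a window of Month 24 plus 8 months. Women who declined to extend stop the gel and contribute their next available mammogram. Section 13.4 provides for measurement timing only for the primary endpoint, and expects fewer than 20 women to be affected.

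The cost is SAP wording and a few lines of programming; the mammograms and readings are the same. The small downside is that the baseline-24 contrast may be less precise than the rebound contrast, with a half-width of about 2.8 points at SD 8 and 3.4 to 4.0 at SD 9.8 to 11.3. The reported interval will make this visible.

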#### 5.5 Dose Modification

For grade 1-2 toxicities, no dose modifications will be made. If a grade 2 toxicity possibly, probably, or definitely related to study drug re-occurs, the gel application will be stopped until the adverse event resolves, then full dose will be reintroduced. If the toxicity re-occurs for a 3rd time, the participant will be taken off study drug. For grade 3 toxicity possibly, probably, or definitely related to study drug, gel application will be stopped until the adverse event resolves, then full dose will be reintroduced. If the adverse event re-occurs, the participant will be taken off study drug. Participants experiencing Grade 4 toxicities of any attribution will be taken off study drug.

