#### 5.6 Adherence/Compliance

5.6.1 The interval from initiation of drug to end of treatment and final mammogram may vary. If a participant has used the gel at least 9 months and 75% of days during that interval, she will be considered compliant.

5.6.2 The following method will be used to monitor each participant’s agent compliance:  
1) Participants will be given a 4-OHT diary and instructed to complete an entry each time a dose is taken (see Appendix D, 4-OHT diary).  
2) Canisters will be weighed when released and also upon return.

If there are discrepancies between the two measures of compliance, the lower compliance value will be used as a conservative estimate of compliance. If the canister weight is the lower of the two compliance values any discarded doses will be considered in the calculation of compliance.

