### 13.4 Primary Objective, Endpoint(s), Analysis Plan

The primary objective of this study is to evaluate the change in percent MD (using Cumulus software) from baseline to the week 52 in women applying 4 mg OHT gel versus placebo based on the intent-to-treat principle. The intent-to-treat population is defined as all participants who are randomized and have MD measurements from both baseline and 52 weeks. The primary analysis will be performed comparing the active group versus placebo group per randomization, regardless of the compliance of each participant.

The percent MD is the MD (percent dense area) that is visually estimated using both the mediolateral oblique (MLO) view and the craniocaudal (CC) view as the proportion of the total breast area that was composed of dense tissue (to the nearest 5%). For the study purpose, the densest breast will be the target lesion for the primary endpoint. Breast biopsy for secondary and exploratory endpoints will be performed in the opposite (non-target) breast.

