At the end of the study, all participants who have MD measurements from both baseline and 52 weeks, regardless of the compliance, will be included in the primary analysis. Change in percent MD of the breast from baseline to 52 weeks will be summarized using descriptive statistics, such as mean, standard deviation, median and range for each arm. With visual assessments of MD from both the MLO and CC views for evaluating the primary endpoint, Hotelling's  $T^2$  test will be used to conduct multivariate hypothesis testing which includes both views. Hotelling's  $T^2$  test represents the multivariate generalization to the independent two-sample t-test in the univariate setting. The correlation and variance-covariance matrix will be assessed to estimate the level of dependency between the MLO and the CC views. The mean change in percent MD at 52 weeks incorporating both the MLO and CC views will be compared between the two groups utilizing Hotelling's  $T^2$  test. Q-Q plots, used to visually assess the assumption of normality, will be constructed for the marginal distributions associated with observations emanating from both the MLO and the CC view. Assuming the mean difference in density between the observations between the 4-OHT and the placebo groups is approximately normally distributed, then the primary analysis will be conducted as previously described. Additionally, a 95% confidence ellipse (simultaneous confidence intervals) for the mean vector containing information from both views will be provided. If the change in density is not normally distributed, then we will try to rescale to achieve approximate normality by using the Box-Cox transformation. In our prior experience evaluating change in density in response to oral tamoxifen, change in density was scaled and raised to the 1.75th power to approximate normality. We will have to determine what power to use in the Box-Cox transformation based on the data that we have on hand. Transformations may be performed when necessary to make the measure of MD close to normal distribution before evaluating the change of MD over time between two groups. If the Hotelling's  $T^2$  test is significant, we will further examine whether the significant difference between the 4-OHT gel group and the placebo group is in the MLO view or the CC view or both. Note that the sample size calculation is based on the two-sample t-test. It provides a conservative estimate of the statistical power because the Hotelling's  $T^2$  test is more efficient than the two-sample t-test.

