### **13.8 Evaluation of Response**

All participants included in the study must be assessed for response to intervention, even if there are major protocol deviations or if they are ineligible.

All of the participants who met the eligibility criteria (with the possible exception of those who did not receive study agent) will be included in the main analysis. All conclusions regarding efficacy will be based on all eligible participants.

Subanalyses may be performed on the subsets of participants, excluding those for whom major protocol deviations have been identified (e.g., early death due to other reasons, early discontinuation of intervention, major protocol violations, etc.). However, subanalyses may not serve as the basis for drawing conclusions

concerning efficacy, and the reasons for excluding participants from the analysis should be clearly reported. For all measurements of response, the 95% confidence intervals should also be provided.

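### A supportive analysis in Section 13.5 adjusts the treatment effect for compliance measured after randomization, so that secondary estimate can be biased; the as-randomized primary analysis is not affected

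*Combined protocol and SAP*

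**What the plan says.** The sentence at issue is in Section 13.5: "The treatment effect will be analyzed by incorporating the longitudinally measured compliance data as a covariate". It is unconditional. It follows two sentences that are labelled sensitivity analyses, but carries no such label itself. No model, estimand, timing rule for the compliance measure or causal method is given. The same section separately says: "The effect of compliance will be evaluated in the per protocol analysis".

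The primary analysis is different. Section 13.4 states: "The primary analysis will be performed comparing the active group versus placebo group per randomization, regardless of the compliance of each participant". On the analysis set it says that "all participants who have MD measurements from both baseline and 52 weeks, regardless of the compliance, will be included in the primary analysis".

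Section 5.6 defines compliance from use during treatment: "If a participant has used the gel at least 9 months and 75% of days during that interval, she will be considered compliant". Section 5.5 ties use to toxicity: for grade 3 events at least possibly related to the drug, and for related grade 2 events that recur, "gel application will be stopped until the adverse event resolves, then full dose will be reintroduced", and further recurrence ends treatment. Section 13.8 says that "subanalyses may not serve as the basis for drawing conclusions" about efficacy, but it describes subsets formed by excluding participants.

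**The concern.** Compliance is an outcome of the trial, not a baseline characteristic. The arm can change it through the toxicity rules in Section 5.5 and through tolerability in general. Section 6.2 reports, for a placebo-controlled study at 4 mg/day, headache in 20% versus 10% and application site reaction in 4% versus 0%, and says that some of these events were judged drug-related. Women who keep applying a gel for a year may also differ from those who do not in ways that bear on density change.

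Once the model holds compliance fixed, the arm coefficient compares active and placebo women who reached the same compliance, possibly for different reasons. That is not the effect of assignment, and it is not the effect in a defined group of adherent women either.

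At stake is a supportive figure that the plan itself calls the treatment effect. Section 2.3 says that the trial will inform a large national study, and an unlabelled adjusted estimate could enter that planning.

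**Working it through.** **1. The plan's own figure.** Section 13.1 assumes decreases of 6% and 2% in percent density (a difference of 4, taken here as percentage points), SD 8 and 64 women per group, "using a two-sided t-test with a significance level of 0.05". The exact t-test power is 80.1%, matching the stated 80%. The standard error of the difference is 8 × √(2/64) = 1.41. None of this involves compliance.

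**2. Size of the shift.** Take a linear model with arm, compliance C and one common slope b for C. The expected adjusted effect is

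adjusted effect = true effect − b × (mean C active − mean C placebo).

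The shift is zero if either b or the arm gap is zero.

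**3. Assumed inputs.** The documents give neither b nor the gap. The illustration sets:
- mean compliance 0.85, and C = 0.85 + gap × arm + 0.075U + noise with SD 0.10, where U is an unmeasured factor with SD 1;
- density change falling by 2 points per SD of U, total SD about 8;
- true effect -4.

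Within-arm SD of C = √(0.075² + 0.10²) = 0.125. Correlation of C with U = 0.075/0.125 = 0.6. Slope b = (−2 × 0.075)/0.125² = −9.6 points per unit of compliance. Within-arm correlation of C with density change = −9.6 × 0.125/8 = −0.15.

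**4. Arm gap.** One anchor from the documents is the 4% versus 0% application site reaction in Section 6.2. If all of that 4% stopped completely, mean compliance would fall by 0.04 × 0.85 = 0.034, or 3.4 points. A 5-point gap is added as a somewhat larger case.

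| Active-arm compliance lower by | Shift | Adjusted effect | Shift / 1.41 |
|---|---|---|---|
| 0 points | 0 | -4.00 | 0 |
| 3.4 points | −9.6 × 0.034 = −0.33 | -4.33 | 0.23 |
| 5 points | −9.6 × 0.05 = −0.48 | -4.48 | 0.34 |

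If the sign of either the slope or the gap reverses, the adjusted effects become -3.67 and -3.52. With a true effect of zero, 64 per arm and a 5-point gap, simulation of this model gave a false-positive rate of about 6% rather than 5%.

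**5. Stronger assumptions.** With r the within-arm correlation and d the arm gap in SD units, the shift is −8 × r × d. For a true effect of -4, r = −0.3 with d = ∓0.25 gives -4.6 or -3.4; r = −0.5 with d = ∓0.5 gives -6.0 or -2.0. Simulated false-positive rates at zero effect were about 7% and 35% respectively. These show how the bias grows; they are not forecasts.

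**6. Different slopes by arm.** In the active arm, compliance also carries drug exposure, so its slope may differ from placebo. With equal mean compliance and one common slope, that alone does not move the average coefficient. It does mean that the arm difference depends on the compliance level, so a model with an interaction or a time-varying compliance term gives an arm coefficient that depends on where it is read. The plan does not say which model is meant.

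**The case against.** The strongest reply is about scope. A reader might infer from the sentence that the trial's randomized comparison is compromised. The documents do not support that: Section 13.4 compares the arms as randomized whatever the compliance, and the sentence sits among secondary and exploratory analyses. This stands in full.

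The second reply is about conditions. A reader might infer that the adjusted estimate is necessarily biased. It is not: with equal mean compliance in the two arms and the same relation to density change, there is no bias. Blinding with a placebo gel of the same composition apart from the drug (Section 6.1) makes a large gap less likely, though it does not exclude one. This also stands.

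The third is about size. Gaps of 10 or 15 points would give -4.96 or -5.44 in the same model, but they equal 0.8 and 1.2 within-arm SDs and no figure in the documents supports them. The Section 6.2 events were mild to moderate. At 3 to 5 points the shift is at most about a third of a standard error.

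A last reply is that Section 13.8 already prevents misuse. That holds only in part. It shows that conclusions are meant to rest on all eligible participants, but its bar covers analyses that exclude women, and a covariate-adjusted model excludes nobody.

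**Conclusion.** The point holds as a limited defect in a supportive analysis. The planned compliance-adjusted arm coefficient conditions on a variable that assignment can affect, has no stated estimand, and can be biased in either direction. The primary analysis, the 80% power and the 64 per group are untouched.

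Under the stated assumptions (true effect -4, compliance-outcome correlation -0.15), a gap of about 3 to 5 points shifts the adjusted effect by about 0.3 to 0.5 points; larger gaps or stronger correlations shift it more. The mechanism follows from the plan. The size does not, because the documents report no compliance data.

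**What to change.** Delete the sentence as an estimate of the treatment effect, or replace it with a descriptive analysis of how compliance is associated with density change within each arm. State in Section 13.5 that efficacy conclusions rest on the as-randomized comparison, and treat the per-protocol result as descriptive too.

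If an effect under adherence is wanted, use randomization as the instrument with a continuous exposure measure, such as the fraction of planned applications used, set to zero drug exposure on placebo. State the assumptions (assignment acts only through drug applied; effect proportional to exposure) and give the confidence interval.

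Do not divide the as-randomized difference by the share meeting the Section 5.6.1 rule, because women below that threshold still receive drug. Assumed example: 70% meet the rule with mean use 93%, the others average 50%, effect proportional to use, as-randomized difference -4.0. Mean use is 0.70 × 0.93 + 0.30 × 0.50 = 0.801. The effect in women meeting the rule is −4.0 × 0.93/0.801 = −4.6, but dividing by 0.70 gives −5.7, an overstatement of 23%. Using mean exposure gives −4.0/0.801 = −5.0 for full use, which is the quantity it claims to estimate.

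The cost is a change of SAP wording, a small amount of extra analysis, and a wider interval for the adherence estimate: in this example the standard error goes from 1.41 to about 1.41/0.801 = 1.76, before allowing for error in measured use.
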